collected in the postprandial state, and this will allow us to evaluate acute postprandial changes in chylomicron LPS content and plasma LPS level, and how these relate to measures of insulin action.

**Specific Aim 2) To determine whether microbiome modulation and an experimental reduction in plasma LPS concentration improve inflammation and insulin action in insulin resistant (obese and T2DM) subjects.**

**Rationale.** Obese and T2DM subjects have alterations in the intestinal microbiome (lower content of beneficial bacteria such as Bifidobacteria) (5), abnormal gut permeability (24, 53), increased plasma LPS (preliminary data) (54, 55), and elevated TLR4 signaling in muscle (38) and monocytes (56). In this Aim we will test whether protecting the intestinal barrier with a synbiotic will restore normal gut permeability, reduce LPS, and ameliorate inflammation (TLR4 signaling) and insulin resistance. To assess the role of LPS independently, also we will reduce plasma LPS concentration with sevelamer.

**Subjects.** 36 (completers) lean ( $BMI < 26 \text{ kg/m}^2$ ) normal glucose tolerant, 36 (completers) obese ( $BMI = 30-37$ ) normal glucose tolerant, and 36 (completers) obese ( $BMI = 30-37$ ) T2DM subjects will be studied. 12 subjects per group will receive the synbiotic (oligofructose plus Bifidobacterium longum), 12 sevelamer, and 12 placebo. We will study an equal number of males and females. Other inclusion and exclusion criteria are similar as described in Aim 1, except that T2DM subjects ( $Hb_{A1c} \leq 8.5\%$ ) will be enrolled. The only antidiabetic drugs allowed are sulfonylureas, due to their minimal effect on muscle physiology and inflammation. Sulfonylureas will be held for 48 h before any procedure to avoid hypoglycemia during fasting.

**Design. Visit 1:** Subjects will undergo a medical history, physical examination, and screening blood tests.

**Visit 2:** Within 3-14 days eligible subjects will return for OGTT.

**Visit 3:** Within 3-14 days subjects undergo blood (LPS) and stool collection and an intestinal permeability test.

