TLR4 regulates numerous signaling cascades, including IKK/NF $\kappa$ B, JNK, ERK, p38 and SOCS. One or more branches downstream of TLR4 might be responsible for the negative effect of LPS on glucose metabolism. Dissecting the role of each of these branches in LPS-induced insulin resistance is beyond the scope of this grant application. Nonetheless, using our primary cell culture system and shRNA, in the future we could perform an in-depth analysis about the contribution of each of these signaling branches.

**Statistical analysis.** Experimental results will be expressed as means  $\pm$  SE. Comparisons of means between all the groups will be done by ANOVA for repeated measures (67). Associations between measures of LPS concentration vs. TLR4 signaling and vs. insulin signaling/sensitivity, within a group, will be determined by Pearson's correlation. For tests of correlation coefficients between groups we will use the Fisher's Z transformation (64). We will also determine the relationship between plasma LPS concentration vs. TLR4 signaling and LPS vs. insulin signaling/sensitivity, by using multiple regression analysis. Scatter plots will be done to look for outliers and to verify linearity. [name] is an experienced biostatistician who will direct the statistical analysis of this study. Based on our preliminary results and data from the literature (36, 65) regarding the variability of these measurements, we calculated that an  $n=12$  subjects/group is required to obtain power  $(1-\beta)$  of 0.80 with a 2-sided test at  $\alpha=0.05$  significance level. Assuming a  $\sim 20\%$  dropout rate, 15

subjects/group would be sufficient to achieve the required group sizes. The following data and power analysis (2-tailed) were obtained from an ongoing human study (PI: [name]).

Variable	Mean±SD Lean	N	Mean±SD Obese	n	Power
LPS Concentration	0.049±0.055	12	0.119±0.014	12	0.99
Insulin Sensitivity (M)	11.3±2.8	12	8.1±2.4	12	0.91
Ins Stim IRS1-P-Y	4.0±1.1	12	0.9±0.6	12	0.99
Variable	Mean±SD Lean	N	Mean±SD T2DM	n	Power
LPS Concentration	0.049±0.055	12	0.130±0.071	12	0.99
Insulin Sensitivity (M)	11.3±2.8	12	4.2±1.7	12	0.99
Ins Stim IRS-1 P-Y	4.0±1.1	12	1.5 ±1.0	12	0.99

For the following variables, data were obtained from published human studies (36, 40, 65).

Variable	Mean±SD Pre-Sevel	N	Mean±SD Post-Sevel	n	Power
LPS Concentration	3.6±3.0	12	1.2±2.3	12	0.99
CRP Concentration	4.8±2.4	12	0.44±0.24	12	0.99
Variable	Mean±SD Placebo	N	Mean±SD Synbiotic	n	Power

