LPS Concentration	87±14	12	54±10	12	0.99

We performed the following calculations (two-tailed) using data from our preliminary *in vitro* experiments:

Variable	Mean±SD Lean Serum	n	Mean±SD Obese Serum	n	Power
MCP-1 mRNA	1.18±0.18	12	2.3±0.6	12	0.88
IL-6 mRNA	0.6±0.06	12	1.2±0.06	12	0.99

**Other specific methods:** **Intestinal permeability test.** Five g lactulose and two g mannitol dissolved in water are ingested, hourly urine and plasma samples are collected for 8 hours, and lactulose and mannitol are analyzed by gas chromatography (66, 67). Lactulose and mannitol permeate only in minimal amounts across the normal intestinal wall and are not metabolized by the body. In disease state, the intestine becomes preferentially permeable to lactulose than mannitol. [name] (Co-I) has previously conducted this test (68).

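### Three of the 11 printed power values do not follow from their own means, SDs and n=12, and a fourth (sevelamer LPS, 0.99) cannot be verified

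*Combined protocol and SAP*

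**What the plan says.** The Statistical analysis paragraph at the end of section D states that 12 subjects per group are required for power 0.80 with a two-sided test at alpha 0.05. It then prints 11 rows of means, SDs, n=12 per column and a power value. No test is named for the tables.

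The lean/obese and lean/T2DM tables are introduced by "The following data and power analysis (2-tailed) were obtained from an ongoing human study". The in vitro table is introduced by "We performed the following calculations (two-tailed) using data from our preliminary" experiments. The sevelamer and synbiotic rows are introduced by "For the following variables, data were obtained from published human studies".

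The rows at issue are:

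- Lean vs obese: "Insulin Sensitivity (M) 11.3±2.8 12 8.1±2.4 12 0.91"
- Lean vs T2DM: "LPS Concentration 0.049±0.055 12 0.130±0.071 12 0.99"
- Lean vs obese serum, in vitro: "MCP-1 mRNA 1.18±0.18 12 2.3±0.6 12 0.88"
- Pre vs post sevelamer: "LPS Concentration 3.6±3.0 12 1.2±2.3 12 0.99"

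**The concern.** A power value is fixed by the means, SDs, sample size, alpha, sidedness and test. The tables give all of these except the test, so the values should be recoverable with a standard two-group calculation, and most are. Three are not, by margins too large for rounding or for the choice between a t and a normal calculation.

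The sevelamer LPS row raises a different problem. Its columns are before and after treatment, so a paired test is the natural reading. Paired power depends on how strongly the two measurements correlate within a subject, and that is not stated.

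These tables are the only calculation shown for n=12, which sets the size of every treatment arm in Aims 1 and 2. The sevelamer row carries most weight because sevelamer is the plan's separate route to lowering LPS. The Aim 2 rationale says "To assess the role of LPS independently, also we will reduce plasma LPS concentration with sevelamer". If that LPS change turned out null, a reader relying on 0.99 would give the result more weight than the printed figures support.

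**Working it through.** **Inputs.** Means, SDs and n=12 as printed in the tables; two-sided alpha 0.05 from the Statistical analysis paragraph.

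**Two-group rows.** Pooled SD = √((s₁² + s₂²)/2); d = |difference in means| / pooled SD; noncentrality = d·√(12/2); power from the noncentral t with 22 degrees of freedom. The normal approximation is shown alongside.

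*Rows that reproduce.* LPS lean vs obese: pooled SD = √((0.055² + 0.014²)/2) = 0.0401, d = 0.070/0.0401 = 1.744, power 0.983 (t) or 0.990 (normal), against 0.99 printed. IRS-1 lean vs obese, M lean vs T2DM, IRS-1 lean vs T2DM, LPS placebo vs synbiotic and IL-6 all exceed 0.999, against 0.99 printed. CRP pre vs post also exceeds 0.999, whether treated as unpaired or as paired at any correlation tried from −0.2 to 0.9. That makes seven.

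*Rows that do not reproduce.*

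| Row | Pooled SD | d | Printed | t | Normal |
|---|---|---|---|---|---|
| M, lean vs obese | √((2.8² + 2.4²)/2) = 2.608 | 3.2/2.608 = 1.227 | 0.91 | 0.82 | 0.85 |
| LPS, lean vs T2DM | √((0.055² + 0.071²)/2) = 0.0635 | 0.081/0.0635 = 1.275 | 0.99 | 0.85 | 0.88 |
| MCP-1 mRNA | √((0.18² + 0.6²)/2) = 0.443 | 1.12/0.443 = 2.529 | 0.88 | >0.999 | >0.999 |

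Unequal-variance (Welch) versions give 0.818, 0.845 and >0.999.

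*Could another convention explain them?*

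- M: a one-sided normal calculation gives 0.913, and a two-sided one using only the smaller SD (2.4) gives 0.904. The first contradicts the two-tailed label and the second ignores the lean SD. With the t test, 0.91 needs about 16 per group (0.900 at 15, 0.919 at 16).
- LPS, lean vs T2DM: one-sided gives only 0.92 (t) or 0.93 (normal), and 15 per group gives 0.92 or 0.94. Two-sided t power of 0.99 needs 24 per group (0.988 at 23, 0.991 at 24).
- MCP-1: 0.88 falls between n=4 (0.844) and n=5 (0.937) per group, far from 12.

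**Sevelamer LPS, paired.** Difference = 3.6 − 1.2 = 2.4. SD of change = √(3.0² + 2.3² − 2·r·3.0·2.3) = √(14.29 − 13.8r). Power is from the noncentral t with 11 degrees of freedom and noncentrality 2.4·√12/SD. The documents give no r, so the range is an assumption.

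| Assumed r | SD of change | Power, 12 pairs | Pairs for 0.80 |
|---|---|---|---|
| 0 | 3.78 | 0.52 | 22 |
| 0.3 | 3.19 | 0.66 | 16 |
| 0.5 | 2.72 | 0.79 | 13 |
| 0.7 | 2.15 | 0.94 | 9 |

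With 12 pairs, power 0.80 needs r of about 0.51 (SD of change at most about 2.70), and 0.99 needs r of about 0.81 (SD about 1.76). Read as two independent groups, the row would have power 0.56.

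**The case against.** The strongest reply is that little follows from the errors. M and LPS lean vs T2DM remain above the 0.80 target at n=12, and MCP-1 was understated. In addition, Aim 2 plans 36 completers in each of the lean, obese and T2DM groups, all with LPS and a clamp before randomisation. Baseline comparisons between those groups could use 36 per group, where the printed inputs give power above 0.99 for both M and LPS. All of this is correct, and it limits the consequence. It does not make values printed against n=12 right.

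Second, the sevelamer value is not shown to be wrong: 0.99 is attainable if r is about 0.81, and the source studies may have supplied a suitable SD of change. This also stands. The point on that row is that the plan leaves out the quantity on which its answer depends. Taken alone, it would be a request for missing detail.

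Third, no test is named for the tables, and the planned comparison of means is repeated-measures ANOVA, so corrected figures to two decimals depend on the method chosen. The overstatement is 9 points (t) or 6 (normal) for M, and 14 or 11 for LPS lean vs T2DM. That is a reason to name the test beside the restated figures. Neither method recovers the printed values. The LPS SDs also exceed their means in two places (0.049±0.055 and 1.2±2.3), which suggests skew, so any normal-theory power for LPS is approximate.

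**Conclusion.** The concern holds. Under a two-sided two-sample t test with equal groups of 12, M lean vs obese is overstated by 9 points (0.82 against 0.91), LPS lean vs T2DM by 14 points (0.85 against 0.99), and MCP-1 is understated by about 12 points (>0.99 against 0.88). None of the three changes the case for n=12.

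The sevelamer LPS value of 0.99 is unsupported rather than refuted. If the within-subject correlation is below about 0.51, 12 pairs fall short of 0.80 for the assumed change of 2.4. This rests on reading the row as paired and on the assumed range of correlations. It should be fixed, but it does not call for a redesign.

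**What to change.** 1. Restate the three values as 0.82 (M, lean vs obese), 0.85 (LPS, lean vs T2DM) and >0.99 (MCP-1), and name the test beside them: two-sided two-sample t, alpha 0.05, 12 per group.
2. For sevelamer LPS, name the paired test, state the assumed correlation or SD of change with its source, and print the matching power in place of 0.99.
3. Unless that source settles the matter, make the claim that 12 subjects give power 0.80 conditional for this row: r of at least about 0.51, or an SD of change of at most about 2.70.

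Optionally, add that a pre/post power figure does not cover the randomised sevelamer vs placebo comparison.

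The cost is wording only. Two figures become less favourable, one becomes more favourable, and the sevelamer figure will depend on the assumption stated. No participants are added, and conduct and analysis do not change.

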**Nutritional Intervention:** After this visit subjects will begin a high or a low fat diet to be ingested for 28 days. The subjects will meet with a nutritionist ([name], RD) who will perform an assessment of macronutrient and energy intake. The meals will be prepared in the Metabolic Kitchen of the BRU. The nutritionist will design the nutritional components and provide dietary education. The high and low fat diets will be designed based on the subjects' usual dietary habits and energy intake to ensure palatability and adherence. The high fat diet will provide 60% of energy from fat (of which 50% from saturated fat), 15% of energy as CHO and 25% from protein. The low fat diet will provide 55% of energy from CHO, 20% from fat, and 25% from protein.

The diets will be isocaloric in relation to the subjects' habitual energy intake. Ready-made meals will be provided to subjects. Oil, butter, heavy cream, eggs, mayonnaise and cheese will be used as the primary fat sources. Subjects will record food intake and will maintain their usual physical activity level.

**Pharmacological/nutraceutical intervention:** On the same day that the nutritional intervention is started, subjects will be randomized to receive, in a double-blind fashion, placebo (maltodextrin, 6 g three times a day), the synbiotic [5 g of oligofructose + 1 g Bifidobacterium longum ( $4 \times 10^{10}$  CFU/g) three times a day], or sevelamer (1.6 g sevelamer + 4.4 g maltodextrin three times a day), for 4 weeks, and discharged home. Sevelamer is obtained from Amgen (Renvela, Cambridge, MA), oligofructose from Orafiti (Tienen, Belgium), Bifidobacterium from Danisco (Copenhagen, Denmark) and maltodextrin from American International Foods (Grand Rapids, MI). Randomization and drug preparation/dispensing is performed by the Research Pharmacist of the BRU. For each dose the powder will be included in identical packets. The subjects from the 3 groups (placebo, synbiotic, sevelamer) will ingest the powder contained in one packet with water 3 times /day for 28 days. Before discharge, subjects are given printed instructions and information about potential side effects.

**Visit 3:** On day 3 of the nutritional intervention subjects will come to the BRU at 7 AM for evaluation of postprandial LPS concentration. Subjects will ingest their breakfast according to their assigned meal plan. Plasma LPS, chylomicron LPS, insulin, and glucose levels are measured at times -30, +60, +120, and +180 min.

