**Visit 4:** On day 24 of the intervention subjects will come to the BRU at 7 AM in the fasting state to undergo stool sample collection and an 8 h intestinal permeability (lactulose/mannitol) testing.

**Visit 5:** On day 28 subjects will undergo whole body DEXA, a euglycemic hyperinsulinemic clamp and indirect calorimetry as described (44, 45). DEXA is performed to examine the effect of the interventions on body composition. At time -30 min a biopsy of the vastus lateralis muscle will be performed. At time 0 min, insulin will be infused at  $60 \text{ mU/m}^2 \cdot \text{min}$  for 180 min. A 2nd biopsy is performed on the contralateral leg at 180 min. After Visit 6, subjects will undergo a washout period of 10-12 weeks. Subjects will not receive any treatment and will maintain their usual (isocaloric) alimentary habits and physical activity level. They will meet every two to four weeks with the nutritionist to monitor their body weight.

**Visit 6:** After the 10-12 week washout period, subjects will come to the CRC for stool collection and plasma LPS measurement. Subject will then begin the second nutritional intervention. If subjects were placed on a low fat diet first, now they will begin a high fat diet, and vice versa. During the second nutritional intervention subjects will receive the same treatment (synbiotic, sevelamer or placebo) assigned during the first intervention.

**Visit 7:** On day 3 of the second nutritional intervention subjects will undergo the same procedure as Visit 3 (plasma LPS, insulin and glucose, and LPS content in chylomicrons, in the postprandial state).

**Visit 8:** On day 24 subjects come to the BRU for stool collection and intestinal permeability testing.

**Visit 9:** On day 28 of the second nutritional intervention subjects will come to the BRU at 7 AM to undergo

[figure not shown]

Figure 15. Study Visit Schedule (Aim 2)

DEXA, insulin clamp, indirect calorimetry, and biopsies of the muscle (2) as described above for Visit 5.

**Analyses.** Plasma LPS (LAL assay,

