**Interpretation and limitations.** Based on prior animal studies we anticipate that the high fat diet will modify the composition of the intestinal microbiota towards an unfavorable microbiome profile. Specifically, we anticipate that there will be a reduction in Bifidobacteria content (22). Since Bifidobacteria protect the integrity of the intestinal barrier (24, 39) we expect that the high fat diet will enhance intestinal permeability, which will lead to increased plasma LPS concentration. If our hypothesis is correct, the elevation in LPS will trigger an inflammatory response in muscle, manifested by increased flux through TLR4 (TLR4-MyD88 association, activation of IKK/NF $\kappa$ B and MAPK). We predict that TLR4 stimulation will result in impaired insulin signaling (enhanced IRS-1 ser phosphorylation and decreased IRS-1 tyr phosphorylation, PI 3-kinase activity, and Akt-AS160 phosphorylation) and reduced peripheral insulin sensitivity (low Rd) during the clamp. Based on studies in rodents (24, 39), we predict that the synbiotic will ameliorate the damage to the intestinal epithelium (*i.e.* permeability) and the rise in plasma LPS caused by the high fat diet, which in turn will blunt the inflammatory response (TLR4 signaling) and improve insulin resistance.

In this Aim the effect of the LPS-binding agent sevelamer also will be assessed to provide an independent way for reducing plasma LPS concentration. Based on previous human studies (35, 36) and our preliminary studies (Fig. 11) demonstrating that sevelamer decreases LPS concentration, and its capacity to bind LPS and inhibit its inflammatory effect (Fig. 12) (41), we anticipate that sevelamer-induced reductions in plasma LPS concentration will lead to reduced inflammatory signaling (IKK/NF $\kappa$ B, MAPK, inflammatory genes) in muscle. Because sevelamer's effect is to reduce LPS, also we anticipate that flux through TLR4 (TLR4-MyD88 association) will be lower. In addition, we expect that the reductions in LPS concentration will predict (correlate with) changes (reductions) in TLR4 signaling and improved insulin signaling and sensitivity.

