**Metagenomics.** The metagenomics experiments will be carried out by [name] (Co-I), as described by his group (69-71). DNA is extracted using a kit from MoBio (Carlsbad, CA) and following the protocol established by the Human Microbiome Project Consortium (72). PCR-amplified 16S rDNA is sequenced using the Illumina HiSeq2000 platform, following the sequencing and data processing protocol designed by Caporaso (73). Taxonomy is assigned to each high-quality read based on the best matching Greengenes database sequence (74). Operational Taxonomic Units are clustered by using the QIIME toolkit (75). For Aim 1, ANOVA and t-test (and their non-parametric versions) and Chi-square/Fisher's exact test are applied to detect taxa with significantly different relative abundance either within the same individuals (*i.e.*, low fat vs. high fat) or between treatments (placebo, synbiotic, sevelamer). Shannon, UniFrac, and Bray-Curtis indices are compared to quantify the community-level variability among the samples within and between individuals. Multiple test corrections (*e.g.*, Benjamini-Hochberg-Yekutieli) are applied to control for false discovery rate. The response variable (microbial composition) is analyzed with the explanatory variables (insulin sensitivity, LPS level, etc.) to evaluate for associations by Generalized linear models. Models also are used for analyzing the influence of explanatory variables on the relative abundance of significantly changing bacterial taxa (or) communities with treatments. For Aim 2, the data analysis and comparisons between groups (obese, T2DM, and lean) and treatments (placebo, synbiotic, sevelamer) are done similarly as in Aim 1.

**Summary/Timetable.** We are very excited about this proposal which will study the role that the microbiome and endotoxemia play a key role in the pathogenesis of insulin resistance. The studies proposed are innovative because the role of the microbiome on insulin resistance is unclear and relevant because they could lead to the development of novel therapies for T2DM. This application describes a 3 year program:

Year 1: Start Aim 1      Year 2: Complete Aim 1; Start Aims 2 and 3      Year 3: Complete Aims 2 and 3

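### On-treatment stool is collected while synbiotic subjects still take B. longum, so the 16S comparison between products may count product in transit as microbiome change

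*Combined protocol and SAP*

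**What the plan says.** **Product.** In Specific Aim 1, the pharmacological/nutraceutical paragraph defines each synbiotic dose as "5 g of oligofructose + 1 g Bifidobacterium longum" at 4×10^10 CFU/g. Subjects "will ingest the powder contained in one packet with water 3 times /day for 28 days". Each subject keeps the same product in both diet periods (Visit 6). Aim 2 uses the same synbiotic for 4 weeks (Visit 4).

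**Stool on treatment.** In Aim 1, Visit 4 states: "On day 24 of the intervention subjects will come to the BRU at 7 AM in the fasting state to undergo stool sample collection". Visit 8, in the second diet period, states: "On day 24 subjects come to the BRU for stool collection and intestinal permeability testing". In Aim 2, the only on-treatment stool is at Visit 5, also on day 24.

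**Stool off product.** Aim 1 has Visit 2 (before treatment) and Visit 6 (after the 10-12 week washout). Aim 2 has Visit 3 (before treatment) and nothing after it ends.

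**Analysis.** Under Other specific methods, Metagenomics, each 16S read goes to its closest match in a reference database. Tests are applied to "detect taxa with significantly different relative abundance either within the same individuals", meaning low versus high fat, or between the three products. Shannon, UniFrac and Bray-Curtis indices are compared, and false discovery rate is controlled. Generalized linear models relate composition to insulin sensitivity, LPS and other variables. Aim 2 is handled in the same way.

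**Expectation.** For the high fat diet, the Aim 1 interpretation section states: "we anticipate that there will be a reduction in Bifidobacteria content".

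The plan describes no strain-specific assay, no rule for reads matching the administered organism and no analysis without them. The limitations text of Aims 1 and 2 does not raise the matter.

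**The concern.** 16S reads assigned by database match do not show whether a B. longum sequence came from a resident organism, from one that has colonised, or from a packet swallowed the day before. With stool taken during dosing, a higher Bifidobacterium share on synbiotic than on placebo, or higher at Aim 2 Visit 5 than at Visit 3, may partly be the product itself.

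This carries into the mechanistic analysis. The plan models taxa that change with treatment against LPS and insulin sensitivity. Product reads that pass that filter would track arm and adherence. If the synbiotic altered LPS or insulin action by any route, Bifidobacterium could then correlate with the outcome without resident flora having changed. The Aim 2 limitations already accept that the synbiotic may act through other routes, such as free fatty acids and cytokines. At stake is the first link of the proposed chain, from synbiotic to microbiome to barrier and LPS to insulin action.

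**Working it through.** The plan gives no effect size, SD or power for any microbiome measure; its synbiotic power row is for LPS. There is therefore no stated figure to reproduce.

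**1. Daily dose (from the documents).** D = 3 × 1 g × 4×10^10 CFU/g = 1.2×10^11 CFU/day. The only bacterial total in the documents is at least 10^14 in the gut (Specific Aims): 1.2×10^11 / 10^14 = 0.12%. That is a standing total, not a daily output, so it sets only a rough scale.

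**2. Product share of stool.** Share = rD / (F + rD), where r is the fraction of product recovered in stool and F the daily faecal bacterial output. Neither is given. Assumed: r from 1% to 100%, F from 3×10^12 to 10^14 per day, one CFU counted as one cell, reads proportional to cells.
- Low end: 0.01 × 1.2×10^11 / (10^14 + 1.2×10^9) = about 0.001%.
- High end: 1.2×10^11 / (3×10^12 + 1.2×10^11) = about 3.8%.

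**3. Apparent rise with resident flora unchanged.** For an assumed resident Bifidobacterium share b, fold = [(bF + rD) / (F + rD)] / b. Example with b = 1%, r = 1, F = 10^13: (1.0×10^11 + 1.2×10^11) / 1.012×10^13 = 2.17%, a 2.17-fold rise.

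**4. Chance that product alone gives p<0.05.** Two-sample t-test on log10 share, 12 per arm (the plan's cell size), assumed SD 0.5, two-sided, before FDR correction; F = 10^13.

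| Assumed resident share | Recovery | Fold | Chance of p<0.05 |
|---|---|---|---|
| 0.1% | 100% | 12.85 | 0.999 |
| 1% | 100% | 2.17 | 0.35 |
| 5% | 100% | 1.23 | 0.07 |
| 0.1% | 10% | 2.20 | 0.36 |
| 1% | 10% | 1.12 | 0.06 |
| 5% | 10% | 1.02 | 0.05 |

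For the 2.17-fold row, the chance is 0.75 at SD 0.3 and 0.17 at SD 0.8. With 12 per arm, 80% power needs a difference of about 1.20 SD. At SD 0.5 that is 0.60 on the log10 scale, about a 4-fold rise.

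**5. Diet contrast within the synbiotic arm.** The same product is taken in both periods and stool is taken on day 24 of each, so a constant contribution does not create a diet difference. It can shrink one. Suppose the resident share truly falls from 1% to 0.5%, a 50% drop, with F = 10^13.
- Full recovery: (1.0 + 1.2)/101.2 = 2.17% falls to (0.5 + 1.2)/101.2 = 1.68%, a drop of about 23%.
- 10% recovery: (1.0 + 0.12)/100.12 = 1.12% falls to (0.5 + 0.12)/100.12 = 0.62%, a drop of about 45%.

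Compared proportionally with placebo, that shrinkage could be read as protection by the synbiotic.

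**6. Diversity indices.** Adding share s of a taxon already present at share p moves a sample's composition by s(1−p) in Bray-Curtis terms: at most 0.012 when s is 1.2%, and at most 0.038 at the 3.8% extreme.

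**The case against.** The strongest reply is that more Bifidobacterium during dosing is the intended manipulation. The Aim 1 rationale describes probiotics as live organisms that colonise, and oligofructose as raising Bifidobacteria that protect the barrier. Sampling stool on the day of permeability testing also suits an association analysis. This stands. It is a good reason to keep the planned analysis, and a reason not to make a community stripped of the genus the main microbiome result.

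Second, the named Bifidobacteria predictions concern the high fat diet (Aim 1) and obese and T2DM subjects (Aim 2), not synbiotic versus placebo, and no microbiome measure is a designated endpoint. That is correct. The between-product comparison and the models of treatment-changing taxa are still in the plan, and they are the exposed analyses.

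Third, the artefact may be trivial. The Aim 1 rationale ranks Bifidobacteria among the dominant gut organisms, which favours the 5% rows of the table. Against that, testing is by taxon after clustering into operational units. The share of B. longum cannot exceed that of its genus, which favours the lower rows. The documents do not settle which applies.

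Fourth, Visit 6 provides an off-product stool. It follows 10-12 weeks without product and exists only in Aim 1, so it can show persistence but cannot separate product from resident flora on day 24.

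**Conclusion.** The concern holds in a limited form. All on-treatment stool is taken during dosing, and nothing in the 16S plan separates ingested B. longum from resident organisms. A Bifidobacterium rise in the synbiotic arm cannot by itself show that the resident community changed. The exposed analyses are those between products that involve the synbiotic, the Aim 2 before-versus-during change in that arm, and the models of treatment-changing taxa against LPS and insulin sensitivity.

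The size is unknown. Product alone could reach p<0.05 with a probability from about 0.05 to 0.999, and that range rests on assumed recovery, faecal output, resident share and SD, none of which the documents give.

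A reader might infer that the synbiotic arm will show microbiome modulation by construction, that the diversity indices must shift, or that the synbiotic versus placebo microbiome comparison cannot answer its question. The documents do not support this. The artefact can be negligible, the Bray-Curtis displacement is small under most of the assumed values, and taxa other than Bifidobacterium are affected only through the shared denominator. Nor is the low versus high fat contrast manufactured by the product. Sevelamer versus placebo and the LPS, permeability, muscle and clamp readouts do not count product reads at all.

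**What to change.** Keep the planned analysis and add the following to the Metagenomics paragraph before sequences are analysed:

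- Run every taxa, diversity and association analysis involving the synbiotic arm a second time. Remove reads assigned to B. longum, or to the genus Bifidobacterium if species is not resolved, from all samples in all arms, and rescale the remainder. Apply this to Aims 1 and 2.
- Report both versions side by side.
- Treat a Bifidobacterium rise in the synbiotic arm as partly a marker of exposure and adherence.
- Claim a change in the resident community only if it is also seen with the administered taxon removed.
- Note in the limitations that a diet-related fall in Bifidobacteria may be diluted in the synbiotic arm.

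The cost is analysis time on sequences already planned; no visit, sample or treatment changes. The downside is that true growth of resident Bifidobacterium fed by oligofructose earns no credit in the taxon-removed version, which is why both are shown.
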